## 4.2 Nonclinical Studies

[figure not shown]
Roflumilast was initially developed as a 500 µg tablet for oral therapy in patients with COPD, and as such has been thoroughly evaluated in nonclinical studies. The safety profile is well-established, and the results of those studies are relevant to the dermal roflumilast (ARQ-151 cream) development program. In addition, since roflumilast N-oxide is a major active metabolite, some studies were conducted on the metabolite. The study sponsor is conducting nonclinical studies in which roflumilast is applied dermally to supplement the information available through the registration and labeling of oral roflumilast and specifically to support dermal clinical trials. Summaries of these new data from dermal studies and existing data from the prior oral/systemic studies follow.

### 4.2.1 Toxicity Summary

The safety profile of oral roflumilast is well-established. An extensive systemic toxicity program that evaluated both roflumilast and its active N-oxide metabolite in multiple species via the oral route of administration was conducted to support registration of the 500 µg tablet for COPD.

The previously-conducted systemic toxicity program included studies to evaluate reproductive toxicity, genotoxicity and carcinogenicity, and the results of those studies are included in the labeling for oral roflumilast.

#### 4.3 Clinical Studies

The formulation of topical roflumilast, ARQ-151 cream, has been evaluated in both psoriasis (through phase 2b) and atopic dermatitis (through phase 2).

##### 4.3.1 Psoriasis Phase 2a

ARQ-151 cream 0.5% and 0.15% have been studied in a phase 2a study (ARQ-151-101; NCT03392168) in adult patients with mild to moderate chronic plaque psoriasis in the United States and Canada. The study included two cohorts. Cohort 1 was a single dose study to 25 cm^2 of psoriatic plaque(s) in 8 psoriasis subjects to determine skin permeation. Cohort 1 subjects were then enrolled, if they met entry criteria, into Cohort 2 of the study. Cohort 2 was a parallel group, double blind, vehicle-controlled study in which ARQ-151 cream 0.5%, ARQ-151 cream 0.15% or vehicle cream was applied QD for 28 days to 89 subjects with 0.5% to 5.0% BSA of chronic plaque psoriasis. Cohort 2 subjects had at least one target plaque of psoriasis of at least 9 cm^2 Target Plaque Area (TPA) in size and with a Target Plaque Severity Score (TPSS)  $\geq 4$ . However, all body psoriasis plaques were treated except for the face, scalp, intertriginous areas and palms/soles. Only safety and pharmacokinetics were evaluated for the single dose Cohort 1 subjects.

In the parallel group assessment (Cohort 2), the Primary Efficacy Endpoint was:

- Difference in mean percent change from baseline at Week 4 in the product of TPSS x TPA between each dose concentration level of ARQ-151 cream and vehicle control. This was assessed as a sum of up to 3 target plaques per subject.

A 10x10 grid of black and white squares, likely a binary matrix or a heatmap. The pattern shows a central black area with white borders, suggesting a central region of high value or activity surrounded by lower values.

### 4.3.2 Psoriasis Phase 2b

ARQ-151 has also been evaluated in a phase 2b study (ARQ-151-201; NCT03638258) in adult patients with chronic plaque psoriasis. ARQ-151-201 was a parallel group, double blind, vehicle-controlled study in which ARQ-151 cream 0.15%, ARQ-151 cream 0.3%, or vehicle cream was applied QD for 12 weeks to 332 adult subjects with 2% to 20% BSA of chronic plaque psoriasis and baseline IGA of Mild or greater.

In ARQ-151-201, the Primary Efficacy Endpoint was:

- Achievement of IGA score of 'clear' or 'almost clear' at Week 6

22 Jan 2021

Confidential

Page 22 of 74

[REDACTED]

[REDACTED]

[REDACTED]

[REDACTED]

[REDACTED]

[REDACTED]

A 10x10 grid of black and white bars representing a 2D convolutional feature map. The bars are arranged in a grid pattern, with varying widths and heights, creating a visual representation of data. The bars are black on a white background, and the grid lines are white on a black background. The bars are of different sizes and shapes, representing different data values or features in the feature map.

#### 4.3.3 Atopic Dermatitis Phase 1 PK Study

ARQ-151 cream has also been evaluated in a 15 day, open label, phase 1, PK and safety study in 16 adult subjects with mild to moderate AD affecting 4 to 8% BSA (Study ARQ-151-102).

#### 4.3.4 Atopic Dermatitis Phase 2

Finally, a parallel group, double blind, vehicle-controlled, phase 2 study (ARQ-151-212; NCT03916081) has recently completed and evaluated ARQ-151 cream 0.05% and 0.15% in the treatment of mild to moderate atopic dermatitis in adolescents and adults with 1.5% to 35% BSA of involvement. .

Overall, ARQ-151 was found to be well-tolerated at both tested doses following once-daily topical application in subjects with mild to moderate AD. ARQ-151 showed a favorable overall safety profile at both tested doses.

#### **4.3.5 Oral Roflumilast Tablet**

Oral roflumilast (DALIRESP®) has been approved globally for the treatment of COPD and has been evaluated in nine phase III/IV randomized double-blind clinical trials ([Wedzicha 2016](#)). Overall, the safety of oral roflumilast has been well established in its targeted population of mostly middle- and upper-aged individuals who currently smoke cigarettes or have smoked them extensively in the past. Adverse events (AEs) reported with roflumilast tablets have been consistent with those expected for oral PDE-4 inhibitors. In a pooled analysis of safety data from 6-month and 1-year clinical trials (N=8630), the most common AEs were diarrhea, weight loss and nausea. Other AEs reported more frequently with roflumilast treatment than with placebo were back pain, influenza, insomnia and decreased appetite ([Michalski 2012](#), [Wedzicha 2016](#)).

In addition to the self-reported cases of weight loss in the 6-month and 1-year oral trials, clinically significant weight loss was also reported in two prospective studies that evaluated weight ([Michalski 2012](#)).

Psychiatric-related AEs were also greater in patients treated with roflumilast tablets (5.9%) compared to those treated with placebo (3.3%). The most common psychiatric-related AEs were insomnia, depression and anxiety. A small number of cases of completed suicide and suicide ideation have been reported in patients taking oral roflumilast in clinical trials and also during post-marketing experience ([Michalski 2012](#)).

The only contraindication to oral roflumilast is use in patients with moderate to severe liver impairment (Child-Pugh B or C), where systemic levels of roflumilast may become elevated.

#### 4.4 Rationale for Development

PDE-4 inhibition is a well validated approach to the treatment of psoriasis.

[REDACTED]

[REDACTED]

[REDACTED]

[figure not shown]
[REDACTED]

[REDACTED]

The safety monitoring practices employed in this protocol (i.e., physical examinations, vital signs/weight, 12-lead ECGs, local skin toleration assessments, hematology, serum chemistry, urinalysis, mood disorder questionnaire, and AE questioning) are adequate to protect the subjects' safety and will detect expected AEs.

Oral roflumilast has now been used for almost a decade in the treatment of COPD exacerbations and its safety record has been well-documented. The known adverse effects of oral treatment in the COPD population (nausea, vomiting, diarrhea, weight loss, psychiatric AEs; see [Section 4.3.4](#)) are readily monitorable. The current protocol is designed to detect these

adverse events and others should they occur, and provides guidance for their management, as necessary, to ensure patient safety.

## **5 STUDY OBJECTIVES AND ENDPOINTS**

### **5.1 Study Objectives**

#### **5.1.1 Primary Objectives**

To evaluate the systemic exposure and characterize the plasma pharmacokinetic (PK) profile of ARQ-151 cream 0.3% and its major N-oxide metabolite, in pediatric subjects with plaque psoriasis involving body surface areas (BSA) of at least 3%.

To evaluate the safety of ARQ-151 cream 0.3% applied QD to pediatric subjects with plaque psoriasis involving BSA of at least 2%.

To explore the efficacy of ARQ-151 cream 0.3% applied QD for 4 weeks to pediatric subjects with plaque psoriasis involving BSA of at least 2%.

### **5.2 Study Endpoints**

#### **5.2.1 Primary Endpoints**

The primary endpoints will be PK, safety and tolerability.

#### **5.2.2 Exploratory Endpoints**

Efficacy will be explored with analyses including:

- Change and percent change from baseline in PASI score at each study visit
- Achievement of a 50% or greater and 75% or greater improvement in PASI score from baseline to each study visit
- Change and percent change from baseline in IGA score at each study visit
- Change and percent change from baseline in I-IGA score at each study visit
- Change and percent change from baseline in BSA score at each study visit
- Change and percent change from baseline in WI-NRS score at each study visit

## 6 INVESTIGATIONAL PLAN

### 6.1 Overall Study Design and Plan

This is a phase 2, open label, maximal usage PK and safety study of ARQ-151 cream 0.3% in pediatric subjects (ages 6 to 11 years old, inclusive) with plaque psoriasis.

At entry, subjects will have at least 2% BSA involvement (excluding the scalp, palms, soles), except for a subset of evaluable subjects who consent to a PK sample for maximal usage evaluation that will have at least 3% BSA involvement (excluding the scalp, palms, soles), and both groups of subjects will have a minimum IGA of Mild ('2').

Subjects who discontinue the study may be replaced.

Subjects/caregivers will apply ARQ-151 cream 0.3% QD for 28 days to all plaque psoriasis affected areas and any newly appearing plaque psoriasis lesions that arise during the study, except on the scalp.

Subjects/caregivers should maintain treatment of areas with study drug for the duration of the study regardless of whether treatable areas clear prior to Week 4. The palms and soles will be treated but will not be counted towards any measurements of efficacy (PASI, IGA, I-IGA, BSA).

Approximately 20 male and female subjects ages 6 to 11 years old with plaque psoriasis:

- All subjects must have at least 2% BSA psoriasis involvement at Baseline
- However, a subset of 6 evaluable subjects who consent to a PK sample for maximal usage evaluation will have at least 3% BSA involvement at Baseline (excluding the scalp, palms, soles).
  - PK evaluable subjects (in the maximal usage subset) are defined as those that have PK results at Week 2. Unevaluable subjects may be replaced.
- All subjects must have at least Mild ('2') psoriasis severity based on IGA at Baseline

### 6.2 Subject Participation

All subjects will participate in screening (up to 3 weeks) and a Treatment phase (4 weeks).

Upon completion of this study, participants may have the opportunity, subject to research site participation, to enroll in an open-label extension study of up to 24 weeks, receiving ARQ-151 cream 0.3% concentration (study ARQ-151-306).

- For subjects who enroll in ARQ-151-306, the Week 4 visit will complete this study (ARQ-151-215).
- Subjects who do not enroll in ARQ-151-306 will complete this study (ARQ-151-215) with the Week 5 Telephone Visit.

### **6.3 Numbering of Subjects**

All screened subjects will be identified by a unique six-digit subject ID number. The first digit will be “5” while the next two digits correspond to the site number (assigned by the Sponsor, e.g., 01 to 05), the last three digits correspond to the sequential order in which the subject is screened for the study (e.g., Subject ID 505-001: first digit fixed at 5, Site 5 (next two digits), subject number 001 screened by that site [last three digits]).

The clinical site is responsible for maintaining a current log of subject ID number assigned to that subject. The subject ID number is required to be entered on all clinical study documentation (e.g., case report forms, labeling of clinical materials and sample containers, investigational product accountability logs, etc.).

### **6.4 Blinding**

This is an open label study, therefore the subjects, the Investigator and clinical personnel will be aware of the treatment an individual has received.

### **6.5 Selection of Study Population**

#### **6.5.1 Inclusion Criteria**

Subjects must fulfill all of the following inclusion criteria to be eligible for participation in the study:

1. Informed consent of parent(s) or legal guardian, and, if age appropriate, assent by the subject, as required by local laws.
2. Males or females, 6 to 11 years old (inclusive).
3. Clinical diagnosis of psoriasis vulgaris of at least 2 months duration as determined by the Investigator or through subject interview. Stable disease for the past 3 weeks.
4. Psoriasis vulgaris on the face, extremities, trunk, and/or intertriginous areas involving at least 2% of BSA (excluding the scalp, palms, and soles).
5. An Investigator Global Assessment of disease severity (IGA) of at least Mild ('2') at Baseline.
6. Subject has adequate venous access for PK sampling in areas not involved by plaque psoriasis and not being treated with ARQ-151 (e.g., back of the hands).
7. Females of childbearing potential (FOCBP) must have a negative serum pregnancy test at Screening (Visit 1) and a negative urine pregnancy test at Baseline (Visit 2). In addition, sexually active FOCBP must agree to use at least one form of highly effective contraception throughout the duration of the trial and for one week after application of the last dose. Highly effective forms of contraception include: oral/implant/injectable/transdermal contraceptives, intrauterine device, and partner's vasectomy. If barrier methods are used (e.g., condom with spermicide, diaphragm with spermicide), then 2 forms of contraception are required in association with spermicide. The use of abstinence as a contraceptive measure is acceptable as long as this is a consistent part of a

lifestyle choice and an acceptable backup method has been identified if the subject becomes sexually active.

8. Females of non-childbearing potential must be pre-menarchal.
9. In good health as judged by the Investigator, based on medical history, physical examination, 12-lead electrocardiogram (ECG), serum chemistry labs, hematology values, and urinalysis.
10. Subjects and parent(s)/legal guardian(s) are considered reliable and capable of adhering to the Protocol and Visit Schedule, according to the judgment of the Investigator.

### **6.5.2 Exclusion Criteria**

1. Subjects with any serious medical or psychiatric condition or clinically significant laboratory, ECG, vital signs, or physical examination abnormality that would prevent study participation or place the subject at significant risk, as judged by the Investigator.
2. Planned initiation or changes to concomitant medication that could, in the opinion of the Investigator, affect psoriasis vulgaris (e.g. beta blockers, ACE inhibitors).
3. Current diagnosis of non-plaque form of psoriasis (e.g., guttate, erythrodermic/exfoliative, palmoplantar only involvement, or pustular psoriasis). Current diagnosis of drug-induced psoriasis.
4. Subjects with any condition on the treatment area which, in the opinion of the Investigator, could confound efficacy measurements.
5. Subjects who cannot discontinue the use of strong cytochrome P-450 CYP3A4 inducers (e.g., efavirenz, nevirapine, glucocorticoids, barbiturates (including phenobarbital), phenytoin, rifampin, and carbamazepine) for 2 weeks prior to Baseline/Day 1 and during the study period.
6. Subjects who cannot discontinue the use of strong cytochrome P-450 CYP3A4 inhibitors (e.g., indinavir, nelfinavir, ritonavir, clarithromycin, itraconazole, ketoconazole, nefazodone, saquinavir, suboxone and telithromycin) for 2 weeks prior to Baseline/Day 1 and during the study period.
7. Subjects who are unwilling to refrain from prolonged sun exposure and from using a tanning bed or other artificial light emitting devices (LEDs) for 4 weeks prior to Baseline/Day 1 and during the study.
8. Subjects who cannot discontinue specific systemic therapies and/or topical therapies prior to the Baseline/Day 1 and during the study period according to [Table 1](#).
9. Current or a history of cancer within 5 years with the exception of fully treated skin basal cell carcinoma, cutaneous squamous cell carcinoma or carcinoma in situ of the cervix.
10. Subjects with any infection requiring oral or intravenous administration of antibiotics, antifungal or antiviral agents within 2 weeks prior to Baseline/Day 1.
11. Known or suspected:

- a. severe renal insufficiency or moderate to severe hepatic disorders (Child-Pugh B or C)
- b. history of chronic infectious disease (e.g., hepatitis B, hepatitis C, or human immunodeficiency virus (HIV))
- c. hypersensitivity to component(s) of the investigational products

12. Subjects with a CDI-2 (parent report) raw score >20 at Screening/Baseline

13. Subjects with a history of a major surgery within 4 weeks prior to Baseline/Visit 1 or subjects who have a major surgery planned during the study.

14. Subjects who are family members of the clinical study site, clinical study staff, or sponsor.

15. Parent(s)/legal guardian(s) who are unable to communicate, read, or understand the local language. Subjects who are unable to communicate or understand the local language, or who display another condition, which in the Investigator's opinion, makes them unsuitable for clinical study participation.

## **6.6 Removal of Subjects from the Study**

Subject participation in this trial may be discontinued for any of the following reasons:

1. Occurrence of any medical condition or circumstance that, in the opinion of the Investigator, exposes the subject to substantial risk and/or does not allow the subject to adhere to the requirements of the Protocol.
2. Occurrence of a treatment-emergent adverse event (TEAE) or considerable worsening of an AE that, in the opinion of the investigator in consultation with the Medical Monitor and Sponsor, represents an unacceptable risk to the subject if he/she continues in the study. The investigator must follow the subject until the AE resolves or satisfactorily stabilizes.
3. Pregnancy
4. Subject's decision to withdraw from the study.
5. Weight loss of >5% if not dieting and after consultation with the Sponsor, at the Investigator's discretion.
6. CDI-2 raw total score of 34, after consultation with a mental health professional, the Sponsor, and at the Investigator's discretion.
7. Requirement for use of prohibited concomitant medication after consultation with the Sponsor and Medical Monitor.
8. Subject's repeated failure to comply with protocol requirements or study related procedures.
9. The subject interrupts trial study drug application for more than 50% of scheduled doses.
10. Termination of the study by the Sponsor, FDA, or other regulatory authorities.

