## 7.9 Treatment Stopping Rules

If a subject has non-cutaneous adverse events of concern, clinically significant laboratory values or any condition that the investigator determines could possibly be related to the study drug, the Investigator should immediately contact the Medical Monitor to discuss if the subject should be discontinued from the study.

Treatment for any individual subject will be discontinued if the subject:

- Experiences a serious adverse event (SAE) or a clinically significant non-serious AE which in the opinion of the Principal Investigator or Medical Monitor warrants discontinuation from the study for that subject's well-being.
- A severe (Grade 3) laboratory abnormality (confirmed by repeat sample and considered related to study drug; see [Appendix 5](#)).

Dosing of study drug for an individual subject may be suspended for safety concerns other than those described above, at the discretion of the investigator if he/she feels the subject's safety may be threatened.

CDI-2 raw total score of 34 should be referred promptly to a mental health care professional and consideration be given to discontinuation from study drug.

A subject that is experiencing suicidal ideation and behavior should be referred immediately to a qualified mental health care provider and consideration given to discontinuation from study drug.

As noted above, study treatment must be discontinued immediately in the event of a female subject's pregnancy.

Treatment should be interrupted:

- If a subject develops an application site reaction with the clinical appearance of an 'irritation reaction', and with a severity of a Dermal Response Score of 5 (erythema, edema and papules) or greater on the scale of Berger and Bowman, treatment should be interrupted for up to one week and may then be resumed if the reaction has, in the opinion of the Investigator, adequately resolved.

Treatment should be discontinued:

- If the reaction reoccurs, treatment should be discontinued permanently, and the subject followed until the reaction resolves.

For cases of suspected allergic contact dermatitis, the medical monitor and sponsor should be notified and there should be discussion about performing patch testing to further evaluate. Patch testing is encouraged in such cases.

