10.9. Children's Depression Inventory 2 (CDI-2)

The CDI-2 assessment will be summarized at Baseline, Week 2, and Week 4. The CDI-2 quantifies depressive symptomatology and is recommended for use in initial evaluation and is appropriate when there is a need for an assessment and robust description of a child's depressive symptoms. This study will use the CDI Parent Report Form. The total score is the sum of the responses for the 17 questions. Total score, functional score, and emotional score will be summarized descriptively at each study visit.

CDI-2 total score is a sum of the 17 questions (individual questions scored as much or most of the time=3, often=2, some of the time=1, Not at all=0; range for score 0 to 51).

- CDI-2 emotional problem scale is a sum of 9 questions (Q1, Q3-6, Q8, Q10-12)
- CDI-2 function problem scale is a sum of 8 questions (Q2, Q7, Q9, Q13-17)

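### The CDI-2 referral and discontinuation rule names the single score 34 with no direction, so read literally it omits the worse scores of 35 to 51

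*Protocol*

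**What the plan says.** Two places in the protocol attach an on-study action to the CDI-2 (parent report) score.

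- Section 6.6, item 6, among the reasons for which participation may be discontinued: "CDI-2 raw total score of 34, after consultation with a mental health professional". Sponsor consultation and investigator discretion are also required.
- Section 7.9: "CDI-2 raw total score of 34 should be referred promptly to a mental health care professional", with discontinuation of study drug to be considered.

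Neither sentence carries a comparator. SAP 10.9 defines the total as the sum of 17 items and gives the "range for score 0 to 51". The entry limit in 6.5.2 item 12 does carry one: "Subjects with a CDI-2 (parent report) raw score >20 at Screening/Baseline" are excluded, which also shows that higher scores are treated as worse. The CDI-2 is scheduled at Screening, Baseline, Week 2 and Week 4.

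**The concern.** A rule meant to catch a child whose depressive symptoms have worsened should apply from the threshold upwards. As worded, this one names a single point. A child scoring 34 is to be referred promptly. For a child scoring 40 the CDI-2 rule gives no instruction.

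This matters because psychiatric events are a named risk of the oral drug. Protocol 4.3.5 reports them in 5.9% of patients on tablets against 3.3% on placebo, with a small number of cases of suicide and suicidal ideation. Section 4.4 counts a mood questionnaire among the monitoring that it considers adequate to protect subjects. The CDI-2 is the only depression scale in the schedule, and this rule is the only on-study action tied to its score. Appendix 6 lets the CDI-2 be collected remotely, so staff may hold a score without having seen the child. Section 6.2 offers an extension of up to 24 weeks on the same cream, so a referral prompt at Week 4 still has a purpose.

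**Working it through.** **Scale.** Protocol Appendix 2 shows 17 items, each scored 0 to 3. Minimum = 17 × 0 = 0; maximum = 17 × 3 = 51. This reproduces the range in SAP 10.9. Scores are whole numbers, so there are 51 − 0 + 1 = 52 possible values.

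**Coverage of the rule.**

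| Reading | Scores covered | Count |
|---|---|---|
| Literal: score equals 34 | 34 | 1 |
| Intended: 34 or greater | 34 to 51 | 51 − 34 + 1 = 18 |
| Omitted by the literal reading | 35 to 51 | 18 − 1 = 17 |

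So 17 of 52 scale values fall outside the literal rule, and they are the 17 highest. These are scale values, not children.

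**Distance from entry.** The highest eligible entry score is 20. Reaching 34 takes a rise of at least 34 − 20 = 14 points; reaching 35 takes at least 35 − 20 = 15.

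**Opportunities.** About 20 children × 2 scheduled post-baseline assessments (Weeks 2 and 4) = about 40 scores. Neither document gives a mean, SD or distribution for the CDI-2, so no expected number at 34 or above can be calculated.

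**Is the missing direction just house style?** Comparable thresholds in the same protocol say otherwise:

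- CDI-2 entry limit (6.5.2 item 12): greater than 20.
- Weight (6.6 item 5, directly above the CDI-2 item): "Weight loss of >5% if not dieting".
- Missed applications (6.6 item 9): more than 50%.
- Skin irritation (7.9): "Dermal Response Score of 5 (erythema, edema and papules) or greater on the scale of Berger and Bowman".

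The Grade 3 laboratory rule in 7.9 also has no upward direction, but it needs none, because the laboratory grades in Appendix 5 stop at 3.

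**Could a symbol have been lost when the PDF was read?** This cannot be fully excluded, but it is unlikely. The same wording occurs in two separate sections, and comparison signs survive elsewhere, including in the item directly above item 6.

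**The case against.** The strongest reply is that nobody would apply the literal reading. To withhold referral at 40, an investigator would have to conclude that 34 is a worry and 40 is not. The entry limit shows that higher is worse, and the 7.9 rule sits under a heading about stopping treatment. That is fair, and it is why the practical effect is probably small.

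Second, little mandatory action is lost. Removal under 6.6 is discretionary and 7.9 only asks that stopping be considered. Prompt referral is the one firm element. This is also correct.

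Third, other provisions reach such a child. Section 6.6 item 1 covers "Occurrence of any medical condition or circumstance that, in the opinion of the Investigator, exposes the subject to substantial risk", and item 2 covers adverse events that pose an unacceptable risk. Section 7.9 asks for immediate contact with the Medical Monitor over non-cutaneous events of concern, lets the investigator suspend dosing for safety reasons beyond those listed, and separately states: "A subject that is experiencing suicidal ideation and behavior should be referred immediately to a qualified mental health care provider". These clauses stand and the child is not unprotected. Each, however, depends on clinical judgement or on a recognised event; none is triggered by a CDI-2 score. A numeric rule exists to prompt action without waiting for that judgement.

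Fourth, this is a wording slip, not a questionable design, and nothing in the documents casts doubt on the value 34. That is accepted: the criticism is of the missing direction only.

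**Conclusion.** The concern holds. Sections 6.6 and 7.9 misstate a paediatric safety threshold: followed exactly, the CDI-2 rule covers 1 of the 18 scores at or above 34 and leaves out the 17 more severe ones. That the comparator is absent is close to certain, subject only to the small chance of a symbol lost in text extraction. That the sponsor meant 34 or greater is an inference, though a strong one.

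The consequence is limited. The main action left unstated for scores of 35 to 51 is prompt referral, general safety clauses remain available, and an eligible child must rise at least 15 points to be affected. How often that would happen cannot be estimated from the documents. SAP 10.9 summarises the scores descriptively and does not use 34, so no planned result changes. The correction should be made because it concerns child safety and costs almost nothing, not because harm has been shown to be likely.

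**What to change.** Write *CDI-2 raw total score of 34 or greater* in both protocol 6.6 item 6 and protocol 7.9, using identical wording, and have the sponsor's clinical experts confirm 34 as the intended cut-off when the text is amended. The cost is a one-line change in each of two sections. Data collection and analysis are unaffected, and the SAP needs no change.
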